7.4. Criteria for Randomization into the Double-Blind Phase

For randomization into the Double-Blind Phase, subjects must meet the following criteria at the completion of the Open Label Titration Phase:

1. Been on a stable dose of CAM2038 q1w for at least 2 consecutive weeks.
2. CAM2038 titrated to a dose that provides analgesia (i.e., 7-day API score of ≤ 4 and at least 2 points below the value at the start of Titration Phase) and is well tolerated for 7 days before randomization.
3. Requires no more than an average of one hydrocodone/acetaminophen 5 mg/325 mg/day during the last 7 days prior to randomization.

4. Demonstrated study medication (CAM2038) compliance $\geq 80\%$ during the previous 14 days.
5. Demonstrated daily compliance with pain intensity scoring for ≥ 11 of the previous 14 days, including the last 3 days prior to randomization.

7.5. Inclusion and Exclusion Criteria for Open Label Safety Extension (For Subjects Continuing from the Randomized Double-Blind Phase)

7.5.1. Inclusion Criteria for Existing Subjects Entering from The Randomized Double-Blind Phase

Subjects who are participating in the Double-Blind Phase of the Study must meet all of the following inclusion criteria in order to be eligible for participation in the Open Label Safety Extension Phase:

1. Completed Double-Blind Phase of the study
2. Signed Informed Consent for Safety Extension

7.5.2. Exclusion Criteria for Existing Subjects Entering from The Randomized Double-blind Phase

1. Clinically significant symptoms, medical conditions, or other circumstances which, in the opinion of the investigator, would preclude compliance with the protocol, adequate cooperation in the study, or obtaining informed consent, or may prevent the subject from safely participating in the study.

7.6. Inclusion and Exclusion Criteria for Open Label Safety Extension (De Novo Subjects)

7.6.1. Inclusion Criteria for De Novo Subjects

Subjects who are not participating in the Double-Blind Phase of the study must meet all of the following inclusion criteria in order to be eligible for participation in the study:

1. Written informed consent provided prior to the conduct of any study-related procedures.
2. Male or non-pregnant, non-lactating female subject, greater than or equal to 18 years old.
3. BMI between 18 and 38 kg/m², inclusive.
4. Treated with daily opioids for moderate to severe chronic pain disorder such as CLBP or osteoarthritis for a minimum of 3 months prior to Screening.
5. On a stable dose of ≥ 40 mg/day of oral morphine or MED during the 14 days prior to Screening.
6. Systolic blood pressure ≥ 100 mmHg and diastolic blood pressure ≥ 60 mmHg.
7. Female subject of childbearing potential who is willing to use a reliable method of contraception during the entire study (Screening Visit to final Follow-up; see Section 9.1.5). To be considered not of childbearing potential, female subjects must be surgically sterile (hysterectomy or bilateral

- oophorectomy, or bilateral tubal ligation with surgery at least 6 weeks before Screening).
8. Male subject who is willing to use reliable contraception.
 9. Willing and able to comply with all study procedures and requirements.

7.6.2. Exclusion Criteria for De Novo Subjects

Same exclusion criteria as for subjects participating in the randomized Double-Blind Treatment Phase (see Section 7.2).

7.6.3. Criteria for Entry into the Titration Phase (for De Novo subjects)

1. After at least a 12-hour washout from the last IR morphine dose, subject should have a COWS ≥ 5 and an API pain score over the past 24 hours ≥ 5 in order to receive a test dose of Buprenex.
2. Passed all baseline criteria, including a normal QTcF, had no change in QTcF >30 ms at 1 hour after the test dose with Buprenex, and had a COWS score <5 after the test dose with Buprenex.

Note:

- Subjects on BPN at Screening are required to participate in the down titration and will undergo a washout period prior to the test dose and first on-study treatment. Subjects entering the study on BPN will not transition to IR Morphine, but will refrain from taking their BPN for 12 -24 hours prior to the test dose to achieve the desired washout period.
- Subjects on BPN at Screening are still required to follow the same Day 1 procedures (e.g., confirmation of pain scores, COWS assessment and Buprenex test dose) as non-BPN subjects.

7.6.4. Criteria for Enrollment into the Open Label Treatment Phase (for De Novo subjects)

1. Been on a stable dose of CAM2038 q1w for at least 2 consecutive weeks.
2. CAM2038 titrated to a dose that provides analgesia (i.e., 7-day API score of ≤ 4 and at least 2 points below the value at the start of Titration Phase) and is well tolerated for 7 days before randomization.
3. Requires no more than an average of one hydrocodone/acetaminophen 5 mg/325 mg/day during the last 7 days prior to randomization.

7.7. Removal of Subjects from Therapy or Assessment

A subject is free to withdraw his/her consent and discontinue participation in the study at any time for any reason. A subject's participation must therefore be terminated immediately upon his/her request, and the reason(s) for discontinuation appropriately documented.

A subject must be discontinued from the study, including the Titration, Double-Blind Phases, and Open-Label Safety Extension Phase, for any of the following reasons:

- Safety reasons, including AEs or significant concomitant illness, injury or urgent surgeries/procedures that would, in the judgment of the investigator, affect assessments of clinical status to a significant extent, require discontinuation of study drug, or both
 - Every attempt should be made to collect samples for a urine toxicology test and BPN blood concentration if a subject experiences a SAE or is discontinued from the study due to an AE. The investigator will remain blinded to the results until the study blind is broken.

- At the request of the Sponsor, regulatory agency, or Institutional Review Board (IRB)
- Subject is lost to follow-up
- Subject treatment allocation is unblinded
- Death of subject

A subject may also be discontinued from the study, at the discretion of the investigator and/or Sponsor, for any of the following reasons:

- Lack of efficacy
- Subject refuses or is unable to adhere to the study protocol visits and procedure
- Major protocol violation
- Pregnancy
- Use of unacceptable concomitant medication(s)
- It is not considered in the best interest of the subject to continue
- Administrative reasons (e.g., termination of enrollment or study)

The investigator must maintain a record of all subjects who discontinue from the study prior to completion. The reason(s) for study discontinuation will be documented. In the event that a subject chooses to withdraw from the study, the Investigator should make a reasonable attempt to obtain and record the reason(s) for withdrawal in as much detail as possible, although the subject is not obligated to provide such reason(s).

In the event that a subject is discontinued while at the clinical site, the early termination procedures shown in the Schedule of Assessments ([Table 6](#), [Table 7](#), [Table 8](#), and [Table 10](#)) should be performed prior to discharge from the clinical site. For any case of early discontinuation, whether or not the subject is at the clinical site, the investigator should ask the subject to return for the early termination procedures, provided that the subject has not withdrawn consent for those procedures. If the subject has not withdrawn consent for procedures, the sponsor can hire a third-party vendor to locate the subject so that the early termination procedures can be performed. If subject refuses to complete early termination procedures, this information will be recorded.

8. TREATMENTS

8.1. Treatment Administration

8.1.1. Transition Phase (after Screening to test dose/Day 1)

Following Screening and confirmation of eligibility, subjects will enter a Transition Phase of up to 2 weeks during which their current opioid dose will be down-titrated by approximately 25% per day to ≤ 80 mg/day MED for subject whose screening MED was ≥ 80 mg/day; or to ≤ 40 mg/day MED for subject whose screening MED was between 40 mg and 79 mg/day. With exception to subjects down-titrating their BPN dosing, subjects will be transitioned to an IR morphine (15 mg QID or 15 mg TID, respectively) for at least 2 days before they enter the Open Label Titration Phase. Following the morphine IR treatment, subjects will enter the Titration Phase. Subjects who were previously on BPN prior to Screening will not need to participate in the morphine-IR phase, but will refrain from taking BPN for 12-24 hours as a washout phase.

8.1.2. Test Dose (Day 1 of Titration)

Subjects are required to refrain from their previous IR morphine treatment for at least 12 hours in order to receive the Buprenex test dose at the clinical site (i.e., Day 1 of the Titration Phase). Subjects will be required to have an API score over the previous 24 hours ≥ 5 , recorded on a paper diary and a COWS score ≥ 5 in order to receive the test dose of Buprenex. The COWS assessment can be performed up to 48 hours after the initial COWS assessment. At that time, subjects will receive an IM injection of 0.30 mg (1.0 mL) Buprenex and will be assessed for any changes in QTcF or withdrawal. ECGs will be taken 15 minutes before and 15 minutes and 1 hour after the test dose. COWS will be assessed at 15 minutes after the test dose.

8.1.3. Titration Phase

After administration of the Buprenex test dose on Day 1, subjects who tolerate the test dose, do not show an increase of > 30 ms in QTcF within 1 hour, and have a COWS score of < 5 within 15 minutes after the test dose will receive their first dose of CAM2038 q1w within 4 hours (+ 30 minutes) after the test dose. Subjects whose screening opioid dose was between 40 mg and 79 mg/day MED will be started on 4 mg CAM2038 q1w. Subjects whose screening opioid dose was ≥ 80 mg/day MED will be started on 8 mg CAM2038 q1w. During the first week of the Titration Phase, subjects who experience significant pain may, at the discretion of the investigator receive a second dose of CAM2038 at their respective dose (4 mg for subjects whose screening MED was 40-79 mg/day; 4 or 8 mg CAM2038 q1w for subjects whose screening Med was ≥ 80 mg/day) on Day 3, 4, or 5. Subjects will then attend clinic visits every week for dosage adjustment. Dose adjustments will be made by increasing or decreasing the dose level of CAM2038 q1w at the scheduled weekly visits (doses of 4 mg, 8 mg, 12 mg, 16 mg, 24 mg, or 32 mg per week).

The maximum dose within a 7-day period cannot exceed 32 mg. Subjects who require doses higher than 32 mg/week will be discontinued from the study. The dosing of CAM2038 q1w will be titrated with the purpose of achieving a stable dose of CAM2038 q1w by the end of the 10-week Titration Phase.

8.1.4. Double-Blind Phase

Subjects who are receiving 4, 8 or 12 mg CAM2038 q1w at the end of the Titration Phase will be randomized to continue their respective 4 mg, 8 mg or 12 mg CAM2038 q1w dosing, or to corresponding placebo q1w for a total treatment duration of 12 weeks (12 injections in the Double-Blind Phase). Subjects who are receiving 16 mg, 24 mg or 32 mg CAM2038 q1w at the end of the Titration Phase will be randomized to CAM2038 q4w (64 mg, 96 mg or 128 mg, respectively) or to corresponding placebo q4w for a total treatment duration of 12 weeks (3 injections in the Double-Blind Phase).

The dose conversions between CAM2038 q1w and CAM2038 q4w are shown below.

- 4 mg CAM2038 q1w = 4 mg CAM2038 q1w or placebo q1w
- 8 mg CAM2038 q1w = 8 mg CAM2038 q1w or placebo q1w
- 12 mg CAM2038 q1w = 12 mg CAM2038 q1w or placebo q1w
- 16 mg CAM2038 q1w = 64 mg CAM2038 q4w or placebo q4w
- 24 mg CAM2038 q1w = 96 mg CAM2038 q4w or placebo q4w
- 32 mg CAM2038 q1w = 128 mg CAM2038 q4w or placebo q4w

CAM2038/placebo q1w must not be administered into a previously injected site for at least 4 weeks. CAM2038/placebo q4w must not be administered in a site previously injected with CAM2038/placebo q4w or with CAM2038/placebo q1w.

During the entire Double-Blind Phase, subjects will be instructed to record their pain intensity ratings before taking rescue medication. Rescue medication will consist of hydrocodone/acetaminophen 5 mg/325 mg tablets, q4-6h prn, not to exceed a total of 6 tablets or a total dosage of hydrocodone/acetaminophen 30 mg/1950 mg/day for subjects whose screening opioid dose was ≥ 80 mg/day. For subjects whose screening opioid dose was between 40 and 79 mg/day MED, the maximum allowable rescue medication will be 15 mg/975 mg/day (three tablets). This dosage limit will provide analgesic rescue medication at a maximum dose to prevent liver toxicity.

In addition, at any time during the Double-Blind Phase, if the subject requires rescue medication above the maximum allowable (hydrocodone/acetaminophen 30 mg/1950 mg/day (six tablets) for subjects whose screening MED was ≥ 80 mg/day; or 15mg/975 mg/day (three tablets) for subjects whose screening MED was between 40 and 79 mg/day), the subject should be asked if they want to continue with the maximum dose of rescue medication or would like to withdraw from the study. If circumstances surrounding discontinuation or withdrawal are unclear, the Medical Monitor should be consulted. If the subject decides to withdraw, the subject should have a final on-treatment visit and then have procedures and assessments completed for any remaining study visits, as specified in the protocol.

Telephone or other contacts made by the site are allowed throughout the course of the study. Subjects should return to the study center according to the schedule specified in this protocol.

One week after the last dose of CAM2038/placebo q1w or 4 weeks after the last dose of CAM2038/placebo q4w, the subjects will attend a Final Study Visit. At the Final Study Visit (or early termination), subjects will be transitioned back to standard care or their treatment prior to study entry. Within 4 weeks after the Final Study Visit, subjects will be contacted by phone to assess AEs and review concomitant medications.

8.1.5. Subjects Randomized to Placebo in the Double-Blind Phase

At the start of the Double-Blind Phase, approximately half of the subjects (170) will be randomized to placebo. These subjects may experience increases in their pain scores and require rescue medication. Sites are encouraged to keep these subjects in the study as long as possible. However, subjects may withdraw consent for participation at any time and for any reason. Subjects who discontinue prematurely may be replaced at the discretion of the Medical Monitor and the Principal investigator, in order to maintain study power.

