During the Titration Phase, subjects will be dosed with CAM2038 q1w until a stabilized dose and adequate analgesic effect has been achieved for at least 2 consecutive weeks prior to randomization to the Double-Blind Phase, in accordance with pre-defined randomization criteria. Subjects whose pain is controlled on 4 mg, 8 mg or 12 mg CAM2038 q1w during the Titration Phase, will be maintained on 4 mg, 8 or 12 mg CAM2038 q1w, or corresponding placebo during the Double-Blind Phase. Subjects whose pain is controlled on 16 mg CAM2038 q1w or higher during the Titration Phase will be transitioned to CAM2038 q4w/placebo during the Double- Blind Phase.

Although there are inherent differences in the PK profiles for weekly and monthly administered products, the CAM2038 q1w and q4w formulations are similar with respect to steady state maximum plasma concentration and trough plasma concentration of BPN. Based on these similarities, the CAM2038 products are expected to be interchangeable when subjects go from weekly to monthly dosing regimens.

Rescue medication, hydrocodone/acetaminophen 5 mg/325 mg, will be provided to help minimize opioid withdrawal symptoms in subjects during the Titration Phase and the Double-Blind Phase (particularly in subjects randomized to placebo). Randomization will be used to avoid bias in the assignment of subjects to treatment, to increase the likelihood that known and unknown subject attributes (e.g., demographics and baseline characteristics) are evenly balanced across treatment groups, and to enhance the validity of statistical comparisons across treatment groups.

A placebo control will be used to establish the frequency and magnitude of changes in clinical endpoints that may occur in the absence of active treatment, as well as to minimize subject and investigator bias. Double-blinded treatment in the Double-Blind Phase will be used to reduce potential bias of subjects and investigators during data collection and evaluation of clinical endpoints.

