During the Double-Blind Phase, the pharmacist will be unblinded to the randomization code to permit dispensation of the CAM2038 or placebo q1w and CAM2038 or placebo q4w syringes to an unblinded staff member who will perform the injections. All other site study personnel, including the investigator and study coordinator, as well as the subjects, will remain blinded to treatment during the Double-Blind Phase of the study. The unblinded staff member will be instructed not to discuss the trial with the blinded staff to ensure the blind is maintained.

The opening of recruitment of subjects for the safety extension is to ensure that a sufficient number of subjects are enrolled to provide required long-term safety data to support the clinical development of CAM2038 for the indication of chronic pain requiring daily treatment with opioids.

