9.6.2. Secondary Efficacy Endpoints

The secondary efficacy endpoints are as follows:

- Change from baseline in the WAWPI scores at Week 12 of the Double- Blind Phase, based on an NRS-11.
- Percentage of subjects with a 30% or greater decrease in API from baseline to Week 12 of the Double-Blind Phase.
- Rescue medication usage (number of days used and total dose) during the Double-Blind Phase.
- Change from baseline to Week 12 of the Double-Blind Phase in EQ-5D-5L score.
- Change from baseline to Week 12 of the Double-Blind Phase in Work Productivity and WPAI score.
- Time to loss of efficacy, defined as discontinuation of study drug for lack of efficacy.

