9.8 ADJUSTMENTS FOR MULTIPLICITY

There is only one primary comparison for the study. The clinical efficacy endpoints listed below are listed in order of hierarchical importance:

1. The primary efficacy endpoint, which is change from baseline in WAAPI at last week of treatment;
2. Change from baseline in the weekly average of daily WPI scores at last week of treatment of the Double-Blind Treatment Phase, based on an NRS-11;
3. Percentage of subjects with a 50% or greater decrease in API from the Open-Label Titration Phase baseline to the last week of treatment of the Double-Blind Treatment Phase;
4. Percentage of subjects with a 30% or greater decrease in API from the Open-Label Titration Phase baseline to the last week of treatment of the Double-Blind Treatment Phase;
5. Time to loss of efficacy, defined as discontinuation from the study or study drug for lack of efficacy;
6. Change from baseline to last week of treatment of the Double-Blind Treatment Phase in PGI-I scale (as assessed by the subject);
7. Change from baseline to last week of treatment of the Double-Blind Treatment Phase in WPAI score;
8. Change from baseline to last week of treatment of the Double-Blind Treatment Phase in EuroQoL Group EQ-5D-5L score; and
9. Rescue medication usage during the Double-Blind Treatment Phase.

The null hypotheses of no treatment difference for the above endpoints will be tested at a two-sided significance level of 0.05 in the order specified. To protect the family-wise two-sided p-value at the 0.05 significance level, the treatment superiority for an endpoint cannot be claimed, unless the superiority claims for all prior endpoints in the list, if any, have been established.

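### Protocol 8.1.5 aims its retention request at placebo subjects, whom blinded sites can identify only by guessing from symptoms; the wording should cover every randomized subject

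*Protocol*

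**What the plan says.** Protocol 8.1.5 has a heading specific to placebo and opens by noting that "approximately half of the subjects (170) will be randomized to placebo". It continues: "These subjects may experience increases in their pain scores and require rescue medication". The retention request follows: "Sites are encouraged to keep these subjects in the study as long as possible". In context, the subjects meant are those on placebo. The section then confirms that anyone may withdraw consent at any time.

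Protocol 6.2 makes the same link when it explains why rescue is provided: to limit withdrawal symptoms, "particularly in subjects randomized to placebo".

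The people addressed do not know the allocation. Apart from the pharmacist and the staff member who injects, Protocol 6.2 states: "All other site study personnel, including the investigator and study coordinator, as well as the subjects, will remain blinded to treatment during the Double-Blind Phase". Protocol 8.6 keeps injecting staff out of subject evaluations.

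The endpoint most exposed is given in Protocol 9.6.2 as "Time to loss of efficacy, defined as discontinuation of study drug for lack of efficacy" and in SAP 9.8, at step 5 of nine, as "Time to loss of efficacy, defined as discontinuation from the study or study drug for lack of efficacy". Protocol 7.7 lists lack of efficacy among the reasons for which the investigator and/or Sponsor may, but need not, discontinue a subject.

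**The concern.** A blinded site cannot know who is on placebo. To act on 8.1.5 it must infer allocation, and the section supplies the signs to use: rising pain and rescue use. That works against Protocol 6.2's own reason for double-blinding, which is to limit bias among subjects and investigators when data are collected and endpoints evaluated.

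Time to loss of efficacy is exposed because its event is a discretionary decision that a site can delay or avoid. If sites work harder to keep subjects they believe are on placebo, placebo events are suppressed and the comparison moves toward no difference. Under SAP 9.8, a failed step 5 blocks superiority claims at steps 6 to 9 (PGI-I, WPAI, EQ-5D-5L, rescue use). Steps 1 to 4 are tested earlier and are unaffected.

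**Working it through.** **Plan's own figure.** Protocol 11.4 and SAP 9.9 size the trial on the primary endpoint only: difference 0.7, SD 2.0, two-sided 5%, 170 per arm.
- Power = Φ(0.35 × √(170/2) − 1.960) = Φ(3.227 − 1.960) = 89.7%.
- n for 90% power = 2 × (1.960 + 1.282)² / 0.35² = 171.5, so 172 per arm.

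The stated 170 and 90% reproduce to rounding. Neither document gives an event rate, hazard ratio or power for time to loss of efficacy, so what follows is illustration.

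**Inputs**
- From the documents: 170 per arm, 1:1 allocation, two-sided 0.05, log-rank test.
- Assumed: proportion with a loss-of-efficacy discontinuation by Week 12 in each arm, exponential event times, and the fraction of events that retention effort prevents.

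**Formulas**
- HR = ln(1 − p_active) / ln(1 − p_placebo)
- Events D = 170 × (p_active + p_placebo)
- Power (Schoenfeld) = Φ(½√D × |ln HR| − 1.96)

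**Main case: 25% placebo, 12% active**
1. No events prevented: HR = ln 0.88 / ln 0.75 = 0.444; D = 170 × 0.37 = 62.9; power = Φ(3.216 − 1.96) = 90%.
2. 20% of events prevented on placebo only (25% becomes 20%): HR = ln 0.88 / ln 0.80 = 0.573; D = 54.4; power = Φ(2.054 − 1.96) = 54%.
3. 20% of events prevented in both arms (20% and 9.6%): HR = ln 0.904 / ln 0.80 = 0.452; D = 50.3; power = Φ(2.814 − 1.96) = 80%.

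**Range over the assumptions**

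| Assumed placebo vs active | Prevented | Placebo only: HR, power | Both arms: HR, power |
|---|---|---|---|
| 25% vs 12% | 0 | 0.44, 90% | 0.44, 90% |
| | 10% | 0.50, 75% | 0.45, 85% |
| | 20% | 0.57, 54% | 0.45, 80% |
| | 30% | 0.66, 30% | 0.46, 74% |
| 20% vs 10% | 0 | 0.47, 76% | 0.47, 76% |
| | 10% | 0.53, 59% | 0.48, 71% |
| | 20% | 0.60, 39% | 0.48, 65% |
| | 30% | 0.70, 21% | 0.48, 59% |

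The placebo-only column assumes that sites guess allocation perfectly and never encourage an active subject to stay. The both-arms column is what results if sites respond to symptoms alike in each arm. Any real effect would lie between them, depending on how far effort differs by arm. In the both-arms column the hazard ratio barely moves; the loss there comes from fewer events.

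**The case against.** A reader might infer that 8.1.5 tells sites who is on placebo, or that time to loss of efficacy is therefore biased. The documents support neither.

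- The text says placebo subjects may worsen. It does not say that active subjects will not, or that worsening reveals allocation.
- While the blind holds, staff see only pain and rescue use, which occur in both arms. An active subject losing efficacy would look the same and could receive the same encouragement. Bias needs effort that differs by arm at equal symptoms, through correct guessing or unblinding. The documented unblinding, at Site 077 (SAP 5.2), is attributed to injecting staff also doing assessments, not to 8.1.5, and that site is outside the mITT Population.
- Other rules are arm-neutral. Under Protocol 8.1.4 any subject needing rescue above the maximum is asked whether to stay or withdraw. SAP 9.3 lets subjects who stop study drug remain in the study, and stopping drug for lack of efficacy is already an event under SAP 9.5.3. Staying in the study therefore need not remove the event.
- Any bias would run against CAM2038, so it could not create a false claim at step 5. Retention also reduces missing Week 12 data for the primary MMRM.
- Investigators in a withdrawal trial expect placebo subjects to worsen whatever the protocol says.

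All of this stands, and it limits the point. It does not explain why the request is confined to one arm: blinded staff cannot follow it as written, and the retention benefit does not depend on naming placebo. The last item does show that correcting 8.1.5 alone would leave the same cue in 6.2.

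**Conclusion.** The defect is one of wording. A retention request addressed to blinded sites names one arm and supplies symptoms as the way to recognise it. That is a needless prompt to guess allocation, acting on a discretionary event that gates steps 6 to 9.

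Bias in time to loss of efficacy is a possibility, directed toward no difference. Its size cannot be derived from the documents. At an assumed 25% versus 12% with 20% of events prevented, power lies between about 54% (effort confined to placebo, the worst case) and about 80% (effort equal in both arms), against about 90% with no events prevented. It would be wrong to read this as a threat to the primary result through the testing sequence, or as favouring CAM2038. The point is a free improvement, not a serious flaw.

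**What to change.** 1. Retitle Protocol 8.1.5 as retention in the Double-Blind Phase.
2. Replace the request with an arm-neutral one, for example: *Sites should make the same effort to keep every randomized subject in the study and completing diaries, regardless of suspected treatment.*
3. Delete the sentence in 8.1.5 that links rising pain and rescue use with placebo, and the matching parenthesis in 6.2.
4. Leave the right to withdraw and all existing discontinuation and rescue rules as they stand.

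The cost is wording only, with no change to procedures, recruitment or analysis, and the retention benefit for Week 12 data is kept. Neutral wording does not recover events that successful retention prevents in both arms; it removes the prompt to treat the arms differently.
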